### 14.6.3. Safety

| Adverse Events   |
|---|
| Duration of AE   |
| 
 
• Calculated as the number of days from AE Start Date to AE Stop Date:               
 
○ AE Start Date = Missing → Elapse Time = Missing
 
○ AE Stop Date = Missing → Elapse Time = Missing
 
○ Otherwise → Elapsed Time = AE Stop Date – AE Start Date + 1
 
○ To report in months, divide the number of days by 30.4375; to report in weeks divide the number of days by 7; to report in years divide the number of days by 365.25.
 
 
 
 |

### 14.6.4. Efficacy

Refer to Section 7 for endpoint derivation and information.

## 14.7. Appendix 7: Reporting Standards for Missing Data

### 14.7.1. Premature Withdrawals

| Element | Reporting Detail  |
|---------|---|
| General | 
 
• A participant enrolled in Part 1 will be considered to have completed the study if they are DLT-evaluable, i.e.:               
 
○ they complete screening assessments, at least 21 days of study intervention and the post-intervention follow-up visit, or
 
○ they discontinue study intervention before Day 21 due to drug related toxicity. Participants who discontinue study intervention before day 21 or who received less than 75% of the intended dose in the first 21 days for reasons other than study drug related toxicity are not considered to have completed the study.
 
 
 
• All available data from participants who were withdrawn from the study will be listed and all available planned data will be included in summary tables and figures, unless otherwise specified.
 
 |

### 14.7.2. Handling of Missing Data

| Element  | Reporting Detail   |
|----------|--|
| General  | 
 
• Missing data occurs when any requested data is not provided, leading to blank fields on the collection instrument:               
 
○ These data will be indicated by the use of a “blank” in subject listing displays. Unless all data for a specific visit are missing in which case the data is excluded from the table.
 
○ Answers such as “Not applicable” and “Not evaluable” are not considered to be missing data and should be displayed as such.
 
 
 
 |
| Outliers | 
 
• Any participants excluded from the summaries and/or statistical analyses will be documented along with the reason for exclusion in the clinical study report.
 
  |

#### 14.7.2.1. Handling of Missing and Partial Dates

| Element        | Reporting Detail  |
|----------------|---|
| General        | 
 
• Partial dates will be displayed as captured in subject listing displays. However, where necessary, display macros may impute dates as temporary variables for sorting data in listings only. In addition, partial dates may be imputed for ‘slotting’ data to study phases or for specific analysis purposes as outlined below.
 
   |
| Adverse Events | 
 
• Imputations in the adverse events dataset are used for slotting events to the appropriate study time periods and for sorting in data listings.
 
• The eCRF allows for the possibility of partial dates (e.g., only month and year) to be recorded for AE start and end dates; that is, the day of the month may be missing. In such a case, the following conventions will be applied for calculating the time to onset and the duration of the event:               
 
○ Missing Start Day: 
 
▪ If study treatment start date is missing (i.e. participant did not start study treatment), then set AE start date = 1st of month.
 
▪ Else if study treatment start date is not missing:
If month and year of AE start date = month and year of study treatment start date then
 
 
 
 
 
 |

| Element                 | Reporting Detail  |
|-------------------------|---|
|                         | 
 
 If AE stop date contains a full date and is earlier than study treatment start date, then set AE start date= 1st of month.
 
 Else set AE start date = study treatment start date.
Else set AE start date = 1st of month.
 
○ Missing Start Day and Month: 
 
▪ If study treatment start date is missing (i.e. participant did not start study treatment), then set AE start date = January 1.
 
▪ Else if study treatment start date is not missing:
If year of AE start date = year of study treatment start date then                             
 
 If AE stop date contains a full date and is earlier than study treatment start date, then set AE start date = January 1.
 
 Else set AE start date = study treatment start date.
Else set AE start date = January 1.
 
 
 
 
 
• Completely missing start dates will remain missing, with no imputation applied. Consequently, time to onset and duration of such events will be missing.
 
• Completely or partially missing end dates will remain missing, with no imputation applied. Consequently, duration of such events will be missing.
 
  |
| Concomitant Medications | 
 
• Completely missing start dates will not be imputed
 
• Partial start dates for any concomitant medications recorded in the CRF will be imputed using the following convention:             
 
○ If day and month are missing:                 
 
– If treatment start date is missing (i.e., subject did not start study treatment), a '01' will be used for the day and 'Jan' will be used for the month;
 
– If treatment start date is not missing                     
 
▪ If year of start date = year of study treatment start date                             
 
· If stop date contains a full date which is earlier than the treatment start date, a '01' will be used for the day and 'Jan' will be used for the month;
 
· else study treatment start date will be used
 
 
 
▪ else a '01' will be used for the day and 'Jan' will be used for the month
 
 
 
 
 
○ If day is missing:                 
 
– If treatment start date is missing (i.e., subject did not start study treatment), a '01' will be used for the day;
 
– If treatment start date is not missing                     
 
▪ If year and month of start date = year and month of study treatment start date                             
 
· If stop date contains a full date which is earlier than the treatment start date, a '01' will be used for the day;
 
· else study treatment start date will be used
 
 
 
▪ else a '01' will be used for the day and 'Jan' will be used for the month
 
 
 
 
 
 
 
• Completing missing end dates will not be imputed
 
• Partial end dates for any concomitant medications recorded in the CRF will be imputed using the following convention:             
 
○ If day and month are missing                 
 
– Earliest of (Dec 31st, date of last contact) will be used
 
 
 
 
 
 |

| Element   | Reporting Detail   |
|---|--|
|   | 
 
○ If day is missing               
 
– Earliest of (last day of the month, date of last contact) will be used
 
 
 
  |
| New Anti-Cancer Therapy/
Radiotherapy/
Surgical Procedures for Efficacy Evaluation (e.g., response rate, time to event) | 
Start dates for follow-up anti-cancer therapy, radiotherapy, and surgical procedures will be imputed in order to define event and censoring rules for progression-free survival, response rate, or duration of response (i.e. start date for new anti-cancer therapy). Dates will only be imputed when a month and year are available but the day is missing. The following rules will be used to impute the date when partial start dates are present on anti-cancer therapy, radiotherapy, and/or surgical procedures dataset[s]:
 
 
• Completely missing start dates will remain missing, with no imputation applied;
 
• Partial start dates will be imputed using the following convention:               
 
• If both month and day are missing, no imputation will be applied;
 
• If only day is missing:                   
 
○ If the month of partial date is the same as the month of last dosing date, minimum of (last dosing date + 1, last day of the month) will be used for the day;
 
○ If the month of partial date is the same as the month of last disease assessment and the last disease assessment is PD, minimum of (last date of disease assessment + 1, last day of the month) will be used for the day;
 
○ If both conditions above are met, the later date will be used for the day;
 
○ Otherwise, a '01' will be used for the day;
 
 
 
 
 
• Completely or partial missing end dates will remain missing, with no imputation applied;
 
 |
| Prior Anti-Cancer Therapy/
Radiotherapy/
Surgical Procedures  | 
Start and end dates are generally not imputed. If start or end dates need to be imputed for an analysis (e.g., to calculate duration of prior therapy or elapsed time as covariates for efficacy analyses), following rules will be applied. Imputed dates are not used for summary of anti-cancer therapy or radiotherapy.
 
 
• If start/end date is completely missing or both day and month are missing, no imputation will be applied
 
• If day is missing for start date, first of the month will be used
 
• If day is missing for stop date,               
 
○ If first dosing date is the first of the month, minimum of (last day of the month, first dosing date) will be used
 
○ Else minimum of (last day of the month, first dosing date - 1) will be used
 
 
 
  |
| Date of initial diagnosis/
Last recurrence/
Last progression  | 
Imputed to derive elapsed time (e.g., time since initial diagnosis, time from last progression); not used for summary of disease characteristics at initial diagnosis
 
 
• If both month and day are missing, first of January will be used
 
• If only day is missing, first of the month will be used
 
   |
| Treatment end date  | 
 
• If there is more than one study treatment, imputation of missing treatment end date will be applied to all applicable treatments following rules below and treatment end date is the latest treatment end date across all study treatments.
 
• In general, completely missing end dates are not imputed, with the following exceptions for imputation of missing treatment end date at interim analyses.
 
• For imputation of missing exposure end date at an interim analysis when subjects are still on treatment, the following conventions will be applied:
 
  |

| Element | Reporting Detail   |
|---------|--|
|         | 

○ If the missing end date is in the last exposure record, the earliest of: the date of the data cut-off, the date of permanently discontinued from the study treatment, the date of withdrawal from the study, or the death date will be used

○ If the missing end date is not in the last exposure record, treatment start date for the record will be used

● The imputed treatment end date will be used to calculate cumulative dose and duration of treatment as specified in Section 14.6.2.

 |

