7.4. Participant and Study Completion

A participant will be considered to have completed the study if they are evaluable with regard to the primary endpoint, and are no longer being followed for progression or survival. Specifically:

A participant enrolled in Part 1 will be considered to have completed the study if they are DLT-evaluable, i.e.:

- they complete screening assessments, at least 21 days of study intervention and the post-intervention follow-up visit, or
- they discontinue study intervention before Day 21 due to drug related toxicity. Participants who discontinue study intervention before day 21 or who received less than 75% of the intended dose in the first 21 days for reasons other than study drug related toxicity are not considered to have completed the study.

Participants enrolled in Part 2 will be considered to have completed the study if:

- they have completed at least 1 interpretable disease assessment

Participants who do not meet the above criteria and are no longer being followed for progression or survival are considered to have discontinued the study.

The End of Study eCRF should only be completed when a participant is no longer being followed.

The study may be considered completed for purposes of a final analysis when 70% of participants enrolled in Part 2 have progressed or died. If available, participants continuing on intervention at the time of final analysis may be offered the option to continue in a rollover trial.

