| Interim Analysis                          | 
 
The interim analysis was planned to be conducted separately for Cohorts 2A and 2B.
 
Timing of the first interim futility analysis:
Cohort 2A: When at least 5 participants become evaluable from each of the MTAP defined subgroups.
 
   |

| Overview of Study Design and Key Features |   |
|--|---|
|  | 
Cohort 2B: When at least 5 participants become evaluable from MTAP proficient subgroup within any histology cohort.
 
 
• The interim futility analysis was planned to be performed every 2-3 months with minimum of 5 additional evaluable participants from the entire Cohort 2A or Cohort 2B.
 
• Within Cohort 2A, one Bayesian hierarchical model was to be used to borrow information between the MTAP defined subgroups. Within Cohort 2B, one Bayesian hierarchical model was to be used to borrow information between the MTAP defined subgroups and between the three indications.
 
• Participants enrolled in Part 1 who were treated at the RP2D of GSK3368715 and have the same disease histology as required for Expansion Cohort 2B were to be included in the analyses as appropriate.
 
• The above interim analyses will no longer be carried out due to the early termination of the study.
 
 |
| Final Analysis                            | 
 
• The study will be considered completed for purposes of a final analysis when 70% of participants enrolled in Part 2 have progressed or died. Due to the early termination during the Dose Escalation (Part 1) phase of this study, final analysis will occur prior to the above definition.
 
   |

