### 14.6.2. Study Population

|  |
|--|
| 
Extent of Exposure
 
 
• Missing treatment stop date will be imputed following rules specified in Section 14.7.2.1.
 
• Daily Oral Drugs 
 
○ Number of days of exposure (duration on study treatment) to study drug will be calculated based on the formula: 
Duration of Exposure in Days = Treatment Stop Date – Treatment Start Date + 1
 
 
○ Participants who were enrolled but did not report a treatment start date will be categorized as having zero days of exposure.
 
○ The cumulative dose will be based on the formula: 
Cumulative Dose = Sum of (Number of Days x Total Daily Dose)
 
 
○ If there are any treatment breaks during the study, exposure data will be adjusted accordingly.
 
 
 
 |
|--|

| Time since Initial Diagnosis   |
|---|
| 
 
• Calculated as the number of days from the Date of Initial Diagnosis:               
 
○ If First Dose Date is missing → Elapse Time = Missing
 
○ If Date of Initial Diagnosis is completely/partially missing → Elapse Time = Missing
 
○ Otherwise → Elapse Time = First Dose Date – Date of Initial Diagnosis + 1
 
 
 
• To report in months, divide the number of days by 30.4375; to report in weeks divide the number of days by 7; to report in years divide the number of days by 365.25.
 
 |

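### SAP 14.6.2 and 14.7.2.1 disagree on missing treatment stop dates, leaving final exposure undefined for anyone still on treatment; where imputation applies, a non-final record with no end date counts as one day

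*SAP*

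**What the plan says.** SAP 14.6.2 (Extent of Exposure) sets no limit by type of analysis: "Missing treatment stop date will be imputed following rules specified in Section" 14.7.2.1. It defines duration as "Duration of Exposure in Days = Treatment Stop Date – Treatment Start Date + 1", and cumulative dose as days times daily dose, summed. It adds that exposure will be adjusted for treatment breaks, without saying how.

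SAP 14.7.2.1 (Treatment end date) is narrower: "In general, completely missing end dates are not imputed, with the following exceptions for imputation of missing treatment end date at interim analyses". The exception opens with: "For imputation of missing exposure end date at an interim analysis when subjects are still on treatment, the following conventions will be applied". Two conventions follow under it:

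- Last exposure record: use the earliest of data cut-off, permanent discontinuation of treatment, study withdrawal and death.
- Any other record: "If the missing end date is not in the last exposure record, treatment start date for the record will be used".

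The section then says: "The imputed treatment end date will be used to calculate cumulative dose and duration of treatment as specified in Section" 14.6.2.

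On timing, SAP 2.3 says that because of early termination the "final analysis will occur prior to the above definition", meaning the milestone of 70% of Part 2 participants progressed or dead. SAP 2.1 stops enrolment and cancels the RP2D and futility analyses. SAP 2.3 still lets participants stay on treatment until progression, unacceptable toxicity or withdrawal of consent. Protocol 7.4 allows that, if a rollover trial is available, "participants continuing on intervention at the time of final analysis may be offered the option to continue in a rollover trial".

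**The concern.** The imputation is written for interim analyses, most of which have been cancelled, and not for the final analysis, which remains. A participant still on treatment at the final cut-off has no stop date, and database cleaning cannot supply a date that has not occurred. Under 14.7.2.1 that participant's duration and cumulative dose cannot be computed. Under 14.6.2 they should be. Two programmers following the SAP could produce different versions of Table 1.13.

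Participants still on treatment tend to have longer exposure than those who stopped, so leaving them out tends to pull the summary down. Exposure by dose level is the background against which adverse events are read.

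The convention for non-final records is a separate matter. Setting the end date equal to the start date credits one day, however long the record ran, although the next record's start bounds it. Multi-day non-final records arise when a dose is held or reduced, so the loss would fall on participants whose dosing was changed.

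**Working it through.** The plan gives no figure to reproduce. The documents give no count of missing end dates, no count of participants on treatment at the final cut-off, and no record lengths. The examples below rest on assumed records and show direction and mechanism only.

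**1. Which rule applies at which analysis**

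| Analysis | Last record, participant on treatment | Non-final record, end date missing |
|---|---|---|
| Dose-escalation review (under Interim Analyses in SAP 3.1; Listing 9 is delivered for it) | Imputed | End = start |
| Final analysis, by 14.7.2.1 | Not imputed | Not imputed |
| Final analysis, by 14.6.2 | Says it will be imputed | Not addressed separately |

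The last two rows are the conflict.

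**2. Final analysis, ongoing participants missing**

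Assume ten durations in days: 21, 28, 42, 56, 56, 56, 70, 84, 112, 224. Suppose the longest are the ones still on treatment and drop out.

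| Missing | Mean | Median | Maximum |
|---|---|---|---|
| 0 | 749/10 = 74.9 | 56 | 224 |
| 1 | 525/9 = 58.3 | 56 | 112 |
| 2 | 413/8 = 51.6 | 56 | 84 |
| 3 | 329/7 = 47.0 | 56 | 70 |

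The mean and maximum fall; here the median does not move.

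**3. Non-final record credited one day**

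End = start gives start − start + 1 = 1 day. Assume 100 mg on Day 1, 100 mg daily from Day 4 for L days with the end date missing, then 50 mg daily for 56 days with no gap.

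- L = 28, true dose: 100 + 28×100 + 56×50 = 5,700 mg. Under the rule: 100 + 1×100 + 56×50 = 3,000 mg, or −47.4%.
- L = 56, true dose: 100 + 56×100 + 56×50 = 8,500 mg. Under the rule: 3,000 mg, or −64.7%.
- Duration by the 14.6.2 formula is unchanged: 87 days for L = 28 and 115 days for L = 56, with or without the missing date. Only the first start and last stop enter. Days summed over records would fall (L = 56: from 113 to 58), which matters only if the unspecified break adjustment works that way.

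The rule is right for the Day 1 dose held as its own record. Protocol Table 2 schedules no dose on Days 2 and 3, so one day is correct.

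**4. Checking a replacement rule**

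Use the day before the next record starts.

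- In step 3 this restores the true dose exactly (5,700 and 8,500 mg).
- Applied to a Day 1 record with no end date, it would credit Days 1 to 3: three doses instead of one.
- With an unrecorded 14-day gap before the next record (100 mg throughout, 56 days after the gap), L = 28 gives 9,900 mg against a true 8,500 mg (+16.5%). L = 56 gives 12,700 mg against 11,300 mg (+12.4%).

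The replacement therefore needs an exception for scheduled non-dosing days, and it depends on interruptions being recorded.

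**The case against.** The strongest reply is that little is at stake. Protocol 6.6 requires start, stop, interruption and reduction dates in the eCRF, and SAP 3.2 places the final analysis after cleaning, so truly missing non-final dates may be few. The one-day convention sits under the interim condition. Read literally, it does not reach Table 1.13, and with enrolment closed further dose-escalation reviews are unlikely. Protocol 7.4 is conditional and concerns a Part 2 milestone; it does not show that any Part 1 participant will be on treatment at the cut-off. The displays are descriptive.

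Most of this stands, and it limits the size of the point. It does not settle the conflict between the two sections, and cleaning cannot create a stop date for someone still being treated.

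A reader might infer more than the documents support:

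- **That the one-day rule shortens duration.** By the 14.6.2 formula it does not.
- **That it could push an adherent participant below the 75% dosing line for DLT evaluability.** Protocol 4.1.1 defines that line by doses received, and nothing derives it from imputed dates. SAP 8.1 also puts dates, scheduled dose and actual dose in the listing, and SAP 14.7.2 leaves missing fields blank there.
- **That affected non-final records are routine.** The one such record the schedule itself implies, Day 1, is credited correctly.
- **That the loss falls mainly on the longest-treated.** This is a fair expectation for participants ongoing at the final cut-off. For non-final records the loss depends on the record's length. No percentage bias can be given without inventing the number of participants and their treatment times.

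**Conclusion.** The point holds in two limited parts.

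First, 14.6.2 and 14.7.2.1 contradict each other for the final analysis. As 14.7.2.1 is written, anyone on treatment at the final cut-off has missing duration and cumulative dose in Table 1.13, which tends to bias the summary downward. The number affected is unknown and could be zero.

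Second, where imputation applies, in practice the exposure listing for dose-escalation review, a multi-day non-final record with no end date is credited one day. This understates cumulative dose, by 47% and 65% in the two assumed examples, and leaves overall duration unchanged.

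Both effects are confined to descriptive exposure displays. No effect on DLT evaluability, DLT summaries or response summaries is shown. The correction is still worth making because it is cheap and removes an ambiguity from required safety reporting.

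**What to change.** Amend SAP 14.7.2.1 so that it agrees with 14.6.2:

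- **(a) Last record.** State that for a participant still on treatment the existing rule (earliest of data cut-off, permanent discontinuation, study withdrawal or death) applies at any analysis, including the final one. Mark ongoing participants in Table 1.13.
- **(b) Non-final record.** Query the date first. If it is still missing, use the day before the next exposure record or recorded interruption, excluding protocol-scheduled non-dosing days, so that a Day 1 single-dose record ends on Day 1. Flag the imputed record in Listing 9.

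Part (b) should accompany part (a), so that extending imputation to the final analysis does not carry the one-day credit with it.

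The cost is a few sentences in the SAP and a small change to the exposure derivation. The downside is that (b) overstates cumulative dose where an interruption was not recorded, by about 12% to 17% in the assumed 14-day-gap example. That is why the query comes first and the record is flagged.
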